9.4.4 SAFETY MEASURES ANALYSIS

The incidence and overall counts and classifications of adverse events that are related to the M•wrap study device and/or protocol procedure will be summarized for the safety population. Summaries will

Confidential

Refer to QMS Number: VAL-PRO-20-0004, Rev G

DCR-00306, Effective – 14-Dec-2022

include incidence and counts overall for AEs and SAEs, by category, severity and by relationship to study device and /or protocol procedure.

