4 STUDY DESIGN

4.1 OVERALL DESIGN

Hypothesis: We hypothesize that non-invasive electrical recordings will permit acquisition of the fetal ECG, maternal ECG and uterine contractions (UC) with proper signal processing and will ultimately support the development of an abdominal fetal monitor that is wireless and unobtrusive. This will be accomplished with the Marani M•wrap wearable garment.

This study is a prospective paired comparison, multi-site trial intended to establish the equivalence of the Marani M•care System with FDA-cleared Doppler FHR, TOCO UC and pulse Ox MHR reference. Subjects who are admitted to triage for potential labor or other inpatient evaluations including but not limited to evaluation for PROM, who are attending in-clinic appointments for Non-Stress Tests (NST), Contraction Stress Test (CST), or at the convenience of the subject will be monitored with both devices simultaneously for FHR, UC, and MHR. Only the data from the CTG device, the standard of care, will be available to the clinical team in a clinical setting. CTG information will not be interpreted in a non-clinic research visit setting. The M•care System data will be compared to that of the simultaneously obtained standard of care CTG data to determine equivalence after the monitoring is completed. No interim analysis is planned.

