7 STUDY DISCONTINUATION AND SUBJECT DISCONTINUATION/WITHDRAWAL

7.1 DISCONTINUATION OF M•WRAP APPLICATION/SUBJECT WITHDRAWAL

Subjects may withdraw from the study at any time. In the event that a subject experiences any adverse events, the protocol may be stopped, and the investigators will analyze the root cause. In addition, fetal wellbeing will be monitored and, if there are any effects considered to be the result of the study, the study may be stopped and there will be routine management of any subject if being seen in a clinical setting. If the subject is being seen in a non-clinic research setting, no CTG data will be interpreted and any adverse events requiring medical attention will be referred to the subject's physician. All adverse events will be followed with relevant records requested until resolution whenever possible. Each site investigator in a clinical setting will be responsible for determining appropriate clinical care. Site clinical staff may also make the decision to withdraw a subject for any other reason.

The reason for withdrawal/discontinuation should be recorded on the appropriate case report form (CRF). Data collected up to the point of withdrawal may be used.

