8.2 SAFETY AND OTHER ASSESSMENTS

During the time any subject is wearing the M•wrap, safety will be monitored. In the clinical setting, a qualified site staff member designated as having appropriate clinical expertise will make determinations regarding appropriate clinical care and care will be provided for any adverse events. If adverse events occur in the non-clinical setting, subjects will be referred to a clinician for treatment as needed.

In the clinical setting, monitoring for fetal wellbeing with standard of care shall be continued. If the subject is being seen in a research visit setting, no interpretations will be made from CTG or the M•wrap.

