9 STATISTICAL CONSIDERATIONS

9.1 ANALYSIS POPULATIONS

For all analysis populations the Hospital and Antenatal groups will be combined. Additional supportive analyses will be conducted for each study group separately.

The safety analyses will be conducted for the Safety Population defined as the population of subjects who enter the setup process (see Section 1.2, Schema) regardless of evaluability for performance measures.

The Performance Evaluable Population will be the primary analysis population for performance measures and will be defined as the population of subjects who:

- Enter the monitoring phase per Section 1.2, Schema;
- Have at least 1 minute of concurrent data with both devices; and
- Do not have any major protocol violations.

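### The pooled safety incidence counts research-only subjects as free of fetal distress, although their CTG is not interpreted and distress visible only on the tracing could not be recognised

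*Combined protocol and SAP*

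**What the plan says.** All references are to the combined protocol and SAP.

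- **Event definition and collection.** Section 10.6 lists fetal distress among the SAE outcomes. Section 8.3.1 collects all adverse events that arise while the M•wrap is worn, whatever the setting.
- **Use of CTG.** Section 4.1: "CTG information will not be interpreted in a non-clinic research visit setting". Section 7.1: "If the subject is being seen in a non-clinic research setting, no CTG data will be interpreted". Section 8.2: "If the subject is being seen in a research visit setting, no interpretations will be made from CTG". By contrast, 8.2 also says: "In the clinical setting, monitoring for fetal wellbeing with standard of care shall be continued".
- **Denominator.** Section 9.1 defines the Safety Population as "the population of subjects who enter the setup process", and adds: "For all analysis populations the Hospital and Antenatal groups will be combined". It promises supportive analyses for each study group.
- **Output.** Section 9.4.4 summarises device- or procedure-related events on the Safety Population. The summaries will "include incidence and counts overall for AEs and SAEs, by category, severity and by relationship to study device" and/or protocol procedure. Section 9.4.1 gives counts and percentages for categorical data. No confidence interval, test or precision target is named for safety.
- **Groups.** Under 9.4.5 the Antenatal group holds both clinic subjects and subjects seen at research-only visits, the latter overseen by a healthcare professional. The subgroup analyses listed there cover primary performance measures, not safety.

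**The concern.** An incidence is interpretable only if everyone in the denominator could have been recorded as a case. For fetal distress seen only on the heart-rate tracing, that condition fails at research-only visits, because nobody reads the tracing for that purpose. Causality grading under 8.3.3.1 does not help, since it starts from an event that has already been noticed. These subjects therefore enter the denominator as event-free by default.

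Safety is half of the stated objective (3.1), and 3.4 expects no related serious events. The likeliest fetal result is therefore zero out of N, and the weight of such a result depends entirely on N. If N includes subjects in whom the event could not be recognised, the report will look like evidence from more pregnancies than actually supplied it.

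**Working it through.** The plan states no fetal event rate, safety interval or research-only share, so there is no safety figure to reproduce.

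**Inputs from the plan.** Recruitment is up to 130, with a minimum of 80 performance-evaluable subjects (synopsis, 9.5). No site may exceed 50% of recruitment (synopsis). The Safety Population is everyone entering setup (9.1), so 130 is its ceiling; 80 is not its definition.

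**Assumption.** Let f be the research-only share. It is not given, so 10% to 50% is used. The site cap limits f to 50% only if all research-only visits come from one site.

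**Step 1: zero events.** The exact two-sided 95% upper limit is 1 − 0.025^(1/n). The pooled value is 1 − 0.025^(1/130) = 2.80%. With n limited to subjects whose CTG is interpreted, n = 130(1 − f):

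| f | n interpreted | Upper limit | Ratio to pooled |
|---|---|---|---|
| 10% | 117 | 3.10% | 1.11 |
| 20% | 104 | 3.48% | 1.25 |
| 33% | 87 | 4.15% | 1.48 |
| 50% | 65 | 5.52% | 1.97 |

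If only 80 subjects entered setup, the pooled limit would be 4.51%, against 4.99% (n = 72, f = 10%) to 8.81% (n = 40, f = 50%). The ratios barely change.

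**Step 2: one event, seen in a CTG-interpreted subject.** Pooled: 1/130 = 0.77% (exact 95% CI 0.02 to 4.21). On interpreted subjects: 1/104 = 0.96% (0.02 to 5.24) at f = 20%, and 1/65 = 1.54% (0.04 to 8.28) at f = 50%.

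**Step 3: bias of the pooled incidence.** Let s be the detection probability at research-only visits relative to clinical visits. With equal true risk, reported/true = 1 − f(1 − s). Let k be the true risk at research-only visits relative to the others. With s = 0, reported/true = (1 − f)/[(1 − f) + fk].

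| f | s = 0, k = 1 | s = 0.5, k = 1 | s = 0, k = 0.5 | s = 0, k = 0 |
|---|---|---|---|---|
| 10% | 0.90 | 0.95 | 0.95 | 1.00 |
| 20% | 0.80 | 0.90 | 0.89 | 1.00 |
| 33% | 0.67 | 0.83 | 0.80 | 1.00 |
| 50% | 0.50 | 0.75 | 0.67 | 1.00 |

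**Step 4: does the planned group split repair this?** Only in part. As defined, Enriched Hospital contains no research-only visits, so its figure would be clean. Antenatal mixes subjects with and without interpreted CTG, so neither its own figure nor the pooled one can be corrected from the planned tables.

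**The case against.** **The plan produces no such statistic.** The safety endpoint is related adverse events, reported as counts and percentages. No interval is planned, and a fetal event would also have to be judged related to a passive electrode garment. A reader might infer that the plan itself overstates precision; it does not, because it states none. What stands is narrower: a reader will draw a bound from 0/N, and N is too large for this event type.

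**Detection is not nil.** A reader might infer that research-only subjects could not have shown a fetal event at all. The documents do not support that. A healthcare professional oversees these visits, adverse events are collected in every setting (8.3.1), they may come to light when a subject presents for care (8.3.4), and records are requested during follow-up (7.1). Only distress visible on the tracing alone is lost. Blinded physicians do review uterine contraction data (9.4.1), but no reading of fetal heart rate for safety is described.

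**Risk may differ by setting.** The clinical subjects include women in latent labour, under induction or with ruptured membranes, while research-only subjects may come from the general population (6.1). If the risk at research-only visits were zero, the pooled incidence would not be understated. This limits the size of the bias, but it does not make unread tracings informative.

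**Section 7.1 against 8.2.** Section 7.1 says "In addition, fetal wellbeing will be monitored", and a reader might infer a conflict with 8.2. There is none: the same sentence confines routine management to the clinical setting, and the next one states the research-setting exception that 8.2 repeats.

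**Conclusion.** The point holds in a limited form. Sections 9.1 and 9.4.4 count research-only subjects as event-free for an SAE outcome that, when visible only on the tracing, cannot be recognised at their visits. No planned safety table separates them.

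The direction is towards understatement, provided that detection is reduced at these visits and the true risk there is above zero. The size cannot be fixed from the documents because the research-only share is missing. Over the assumed 10% to 50%, the zero-event upper limit rises by a factor of about 1.1 to 2.0. A halving of the reported incidence needs a 50% share, no detection at all and equal risk, none of which the documents establish. Performance endpoints and maternal or skin events are unaffected.

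**What to change.** In 9.4.4:

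1. Tabulate related AEs and SAEs by visit setting (clinical against research-only) as well as pooled.
2. For fetal events, add the incidence among subjects whose CTG was clinically interpreted while the M•wrap was worn, with an exact 95% CI and that denominator shown.
3. List any fetal event recognised by other means, in any setting, so that the restricted denominator drops nothing.
4. State that fetal events detectable only from the tracing were not ascertainable at research-only visits. A broader statement that fetal events are not ascertained there would contradict 8.3.1.
5. Keep maternal and skin events on the full Safety Population.

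The cost is a few lines of SAP text and one extra table split. Section 9.4.2 already summarises appointment or admission type, so little or no new data should be needed. Subject procedures do not change. The downside for the sponsor is a less favourable fetal safety bound.

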9.4.5 ADDITIONAL ANALYSES AND CONSIDERATIONS

The following analyses will be conducted as supportive analyses to the primary analyses described in Section 9.4.3:

Subgroup Analyses

Primary performance measures will be presented separately by the following subgroups and evaluated for consistency:

- BMI strata (Low \leq 29; Medium $>$ 29 and \leq 35; High $>$ 35 and \leq 45)
- Race
- Study group (Antenatal and Enriched Hospital), defined as follows:
 - Antenatal – includes subjects evaluated per obstetric standard of care in the clinic/office environment and subjects completing research-only visits in a non-clinic setting with oversight by a healthcare professional. Subjects with premature rupture of membrane (PROM) will also be included.
 - Enriched Hospital – includes subjects in early (latent) phase of labor with suspected or confirmed uterine contractions, and subjects who are being induced for labor.

Primary performance measures data will be analyzed for all subjects regardless of major protocol deviations, where available.

Missing Data and Invalid Data

Only valid synchronized data will be analyzed. Missing performance measurement data will not be imputed. Determination of invalid signals will be addressed by data management according to written work instructions.

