Study Success Criteria	
Primary Performance Goals:
 
• M•care FHR limit of agreement (LOA) within the performance goal of 15 beats per minute (bpm) of FHR measured with CTG.• M•care MHR limit of agreement (LOA) within the performance goal of 10 beats per minute (bpm) of MHR measured with CTG. 
Secondary Performance Goal:
 
• M•care UC detection sensitivity with a performance goal of greater than or equal to 80% agreement.
Study Methodology	
Subjects will be assessed for study suitability based on the stated inclusion and exclusion criteria. Once informed consent is obtained, the study monitoring systems will be applied to the subject's abdomen.
 
Recording session:
 
• Prior to deployment of the M•care system, subjects will be monitored with the external CTG device for fetal heart rate detection and the CTG pulse oximeter for maternal heart rate signal confirmation.• The M•wrap will be modified to allow positioning of the CTG transducers for simultaneous recording with both devices for FHR, MHR and UC (refer to Appendix 1).• The modified M•wrap will be secured to the subject's abdomen and the subject will be monitored in stationary position for the duration of study recording session while following the M•wrap Instructions for Use.• Data is transmitted from the M•care system application to the Marani Cloud. There, the Marani proprietary signal processing is performed, and the data are analyzed to identify clean MHR, FHR and UC signals. Comprehensive analysis of the values will be performed offline. 
Each recording session will last for a minimum of 60 minutes and no longer than 120 minutes. Following the completion of the session, the study staff will remove the M•care monitoring system from the maternal abdomen and the study session will be concluded.
 
The equivalence of the M•care System data will be compared to that of the simultaneously obtained reference device data. Complete monitoring strips will be obtained for each device and monitoring session to allow comparison for determination of equivalence. Comparison assessments between the M•care and CTG device will evaluate FHR, MHR and UC. Blinded review of UC data will be conducted by two physicians experienced in obstetrics; in the event of discordance, a third blinded reviewer will serve as an adjudicator.

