	
At all times, the M•care system shall be considered a research device. In the clinical setting (i.e., not a research-only visit), the M•care system is an adjunct to routine care and not a replacement for routine or urgent care needs. Only the data from the standard of care reference devices will be available to the clinical care team. Data recorded by the M•care system will not be accessible by study team members, thus clinical decisions for all subjects will solely be based on standard of care practices.

Statistical Considerations	
Success Criteria: Study success will be based on the following two primary performance goals: Primary performance goal, FHR The primary performance goal will be met if the 95% confidence interval for the 95% limits of agreement (LOAs) between the M•care System and the standard of care reference device for the primary performance endpoint, FHR are within the performance goal interval of [-15, 15] bpm. Primary performance goal, MHR The primary performance goal will be met if the 95% confidence interval for the 95% limits of agreement (LOAs) between the M•care System and the standard of care reference device for the primary performance endpoint, MHR are within the performance goal interval of [-10, 10] bpm. Secondary performance goal, UC The performance goal for the secondary endpoint, UC, will be met if the lower bound of the 2-sided 95% confidence interval for sensitivity is greater than 80% for M•care as compared to standard of care reference device. Sample Size Justification: A sample size of N=80 evaluable subjects with an average of 60 minutes of comparative device data will provide adequate power to establish equivalence between M•care and standard of care in the primary performance measurements of FHR and MHR, and the secondary performance measurement of UC event sensitivity. It is anticipated that up to 130 subjects from a minimum of 3 sites may be recruited to allow for inability of approximately 30% of subjects to complete the Monitoring Session per the study protocol. Background Mhajna et al reported the mean difference and (95% LOA) [SD] between INVU and standard of care reference CTG for FHR and MHR measurements as -0.30 bpm (-8.84, 8.24) [SD=4.36] and 0.28 (-5.30, 5.86) [SD=2.85], respectively.¹ Furthermore, Hayes-Gill et al² and Mhajna 2021^{3,4} reported positive agreement (e.g., sensitivity) rates vs IUPC in uterine contraction events of 88%.

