The primary performance endpoint is M•care MHR limit of agreement within 10 beats per minute (bpm) of MHR measured with Pulse Oximetry MHR with the CTG. It has been shown that a woman's heart rate increases by an average 10 to 20 bpm during pregnancy.¹⁶ The mean heart rate at 34-42 weeks' gestation was reported by Van Oppen et. Al as 92 ± 1 .¹⁷ Sherman, et. al showed that heart rate variability is 15.8 ± 1.8 during the latent phase and 12.7 ± 1.1 during the active phase of the first stages of labor.¹⁸ Other clinical studies have chosen an increase or decrease in heart rate of ≥ 10 beats per minute (bpm) at the peak of a contraction as compared to 10 seconds before the contraction to be regarded as either an acceleration or deceleration.¹⁹ As such, these reports support that a 10 bpm LOA is a clinically acceptable range to recognize common clinical phenomena including accelerations and decelerations. Additional considerations for tachycardia and bradycardia have been considered. Odendaal et al. reported that tachycardia is defined as a "rate of at least 100 beats per minute under resting conditions" while the definition of bradycardia in pregnancy "has not been standardized."²⁰

Uterine Contractions

Uterine contractions are identified based on the tracings output by the relevant device; knowledgeable readers interpret the tracings to identify the contractions. The outcomes are binary: either the event happened, or it did not. To evaluate the performance of this binary outcome, our success criterion is to obtain results consistent with cleared devices with similar technologies such as the Monica AN24 per K101801 510(k) Summary, Monica Novii Instructions for Use (107-PT-005-EN rev P), and TOCO¹³ in general.

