9.2.2 SECONDARY PERFORMANCE MEASURES

The secondary performance measure is Uterine Contractions (UC) sensitivity as measured by the M•care System versus the standard of care CTG device. Sensitivity is defined as the proportion of UC events identified by standard of care that are simultaneously (e.g., within 30 seconds) identified by the M•care System.

 MARANI	MARANI PRENATAL CONNECTED CARE (M•care) Safety and Effectiveness Study (M•CARE SE Study)	
Protocol Number: MH-001	Revision Number: G	Page 28 of 46

Hypothesis testing for UC sensitivity will only be conducted if the primary performance measures (i.e., equivalence in FHR and MHR) are met.

Additional UC endpoints as measured by the M•care System versus standard of care CTG device, include:

- Positive predictive value (PPV) defined as the proportion of UC events identified by both the M•care System and standard of care out of those that are identified by the M•care System.
- False Positive Rate defined as the proportion of UC events identified by the M•care System that are not identified by the standard of care.

No hypothesis is planned for the PPV and false positive rate endpoints.

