9.4 STATISTICAL ANALYSIS

9.4.1 GENERAL CONSIDERATIONS

Each recording session will last for a minimum of 60 minutes and no longer than 120 minutes with multiple observations per subject for FHR and MHR and UC events. For analysis of UC events, blinded review will be conducted by two physicians experienced in obstetrics. In the event of discordance, a third blinded reviewer will serve as an adjudicator.

Confidential

Refer to QMS Number: **VAL-PRO-20-0004, Rev G**
DCR-00306, Effective – 14-Dec-2022

Descriptive statistics will include n, mean, median, standard deviation, minimum and maximum for continuous data and n and percentages for categorical data. To account for the correlation among multiple measurements within subjects, MMRM (mixed-effect model repeated measures) statistical methods will be utilized for the primary analyses, with bootstrap resampling methods conducted as a supportive analysis. Unless otherwise specified all statistical tests will be conducted at a 2-sided alpha of 5%.

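### Sections 9.2.2 and 9.4.5 imply different denominators for the tested UC sensitivity when M•care has no usable signal, and no passage reconciles them

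*Combined protocol and SAP*

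**What the plan says.** On the measure, section 9.2.2 (repeated in 3.3) reads "Sensitivity is defined as the proportion of UC events identified by standard of care that are simultaneously" identified by M•care, with a 30-second window given as an example. The denominator carries no condition on the M•care signal. The synopsis sets the goal as met if "the lower bound of the 2-sided 95% confidence interval for sensitivity is greater than 80" percent. The test is run only if the FHR and MHR goals are met.

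On which data enter, section 9.4.5 says "Only valid synchronized data will be analyzed. Missing performance measurement data will not be imputed". It is not limited to heart rate. It continues: "Determination of invalid signals will be addressed by data management according to written work instructions". Those instructions are not part of the protocol. The synopsis (Study Methodology) says that after signal processing "the data are analyzed to identify clean MHR, FHR and UC signals", so UC is among the screened signals.

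On how contractions are read, the synopsis says "Complete monitoring strips will be obtained for each device and monitoring session". Section 3.5 says "knowledgeable readers interpret the tracings to identify the contractions", and 9.4.1 says "For analysis of UC events, blinded review will be conducted by two physicians experienced in obstetrics", with a third reader for discordance. None of these says how a blank or invalid M•care segment is to be scored.

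Section 9.1 makes a subject evaluable with 1 minute of concurrent data, so a subject with long M•care loss can stay in the analysis.

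**The concern.** The two sections treat the same event differently. Take a contraction that is clear on the TOCO trace while M•care is recording but yields nothing usable. Under 9.2.2 it is in the denominator and was not detected. Under 9.4.5 it is not valid synchronized data and drops out of numerator and denominator alike.

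The first answers what share of standard-of-care contractions M•care finds. The second answers what share it finds when its signal is good. Both are legitimate questions, but only the first is the stated definition. The test has a pass/fail bound, so the same strips could pass on one reading and fail on the other. A pass on the valid-only reading, reported under the 9.2.2 definition, would claim more than was shown.

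Planned outputs would not reveal the gap. The 2x2 UC table (9.4.3), the device-deficiency forms (8.3.2) and the listing of excluded subjects (9.4.2) show some loss. None gives the share of CTG-valid recording time with valid M•care output.

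**Working it through.** **Inputs from 9.5 and the synopsis.** 80 evaluable subjects, an average of 3 UC events each, sensitivity 90%, goal 80%, within-subject correlation 0.5, two-sided 95% interval. The loss rate L is an assumption, because the documents give none.

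**The plan's own figure.** The design effect is 1 + (3 - 1) x 0.5 = 2, so the effective number of events is 240 / 2 = 120.
- Null variance: (0.10 - 1.96 x sqrt(0.16/120)) / sqrt(0.09/120) = (0.1000 - 0.0716) / 0.0274 = 1.04, power 85.0%.
- Wald: 0.10 / 0.0274 - 1.96 = 1.69, power 95.5%.
- Exact binomial (at least 105 of 120): 85.6%.
- Simulation with an exchangeable model and logit interval: 82.7% with exactly 3 events each, 80.3% with Poisson counts.

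The stated power above 80% is reproduced.

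**Direction.** Let D be detected contractions, M those missed on a valid signal and L those during absent output. Valid-only sensitivity is D/(D + M); the 9.2.2 value is D/(D + M + L). The first is larger whenever D and L are both positive.

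**Size, holding the 9.2.2 value at exactly 80%.** The valid-only value is 0.80/(1 - L). Pass probabilities are from simulation: 80 subjects, beta-binomial detection with correlation 0.5, cluster-robust 95% interval. The ranges cover logit and Wald intervals, fixed and Poisson event counts, and independent or clustered loss.

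| Assumed loss | Valid-only sensitivity | Passes, valid-only | Passes, 9.2.2 |
|---|---|---|---|
| 5% | 0.80/0.95 = 84.2% | about 18-28% | about 2-5% |
| 10% | 0.80/0.90 = 88.9% | about 58-80% | about 2-5% |
| 15% | 0.80/0.85 = 94.1% | about 95-99% | about 2-5% |

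**Effect on the stated power.** Section 9.5 does not say which sensitivity its 90% is.
- If it is detection in valid data, the 9.2.2 value is 0.90 x availability: 88.2%, 85.5%, 81.0% and 76.5% at 98%, 95%, 90% and 85% availability. It reaches 80% at availability 0.80/0.90 = 88.9%, that is about 27 of 240 contractions lost. Power under 9.2.2 at 95% availability is about 30-50%.
- If it is sensitivity over all CTG contractions, loss is already inside the 90%. Power under 9.2.2 at 95% availability is about 85-96% with independent loss, and lower if loss is concentrated in a few subjects.

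**The case against.** The strongest reply is that the sections are complementary: 9.2.2 defines the measure and 9.4.5 says which data feed it. Several phrases lean that way: simultaneous identification in 9.2.2, concurrent data from both devices in 9.1, comparative device data in 9.5. The unseen work instructions may also contain the rule. This has force, and 9.4.5 alone does favour exclusion. But if it governs, the tested quantity is conditional on a valid M•care signal, and 9.2.2 does not say so. The denominator of a pass/fail test belongs in the plan.

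Three stronger readings are tempting and not supported.
- A reader might infer that exclusion can only raise the estimate. That holds for the crude proportion where output is absent. Section 9.4.5 also removes invalid data, and a contraction in a segment flagged invalid could still have been matched within 30 seconds; dropping it would lower the estimate. With the correlation re-estimated in the model, one reversal appeared in 2,000 simulated trials in one scenario.
- A reader might infer that the UC test is badly underpowered or needs more subjects. That follows only if the 90% means detection in valid data, which 9.5 does not say.
- A reader might infer that the choice will be made after the results are seen. Nothing in the documents shows this.

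**Conclusion.** The conflict in the text is real and unresolved. Applied as written, 9.4.5 tests a sensitivity conditional on usable M•care signal, while 3.3 and 9.2.2 state one over all standard-of-care contractions. At an assumed 10% loss, a device whose all-contraction sensitivity is exactly 80% would meet the goal about 58-80% of the time on the valid-only reading, against about 2-5% under 9.2.2.

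That size rests on an assumed loss rate, on lost contractions being unmatched, and on simulation models that stand in for the plan's binary MMRM. With little loss the two readings nearly coincide. The effect on the stated power cannot be fixed until 9.5 says what its 90% means.

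A reader might extend the point to study success as a whole. The documents do not support that: UC sensitivity is secondary and gated, and this point shows no effect on the FHR or MHR result. It is a worthwhile, inexpensive clarification that limits what a UC pass can be taken to show.

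**What to change.** Before data review, amend 9.2.2 (with 3.3) and 9.4.5 so that they name the same denominator, and give the UC readers the same scoring rule. Whichever estimate is tested, report together:

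- (a) sensitivity with CTG contractions during absent or invalid M•care output counted as not detected. Restrict this to active M•care recording segments with a valid TOCO trace, and leave out planned gaps between data collection initiations (6.1) and time when the M•wrap is removed or repositioned (8.1);
- (b) the valid-only sensitivity;
- (c) the percentage of CTG-valid recording time with valid M•care output.

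If (b) is the tested estimate, say in 9.2.2 and in the claim that sensitivity is conditional on a valid M•care signal. If (a) is tested, note that its restrictions also narrow the literal 9.2.2 definition. In 9.5, state whether the 90% is detection in valid data or over all CTG contractions.

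The cost is wording and some programming on strips already recorded, including time stamps for recording segments and wrap removal. The reported sensitivity may look less favourable. No change in enrolment is proposed.
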